## 1.0 Objectives

### 1.1 Purpose:

The primary objective of this study is to test the feasibility, acceptability, safety and targeted outcomes of a 3-month hatha and restorative yoga intervention to decrease sedentary behavior (primary outcome), stress and blood pressure in 60 sedentary (<30 minutes of moderate-to-vigorous PA per week) African-American women. The proposed study has four aims:

Aim 1: To refine a promising and innovative intervention to enhance its feasibility. Based on our previously developed intervention, I HEART Yoga!, and subsequent experience, we will refine intervention strategies to incorporate findings from the pilot research and theoretically ground the intervention using an integrated model incorporating constructs from the Social Cognitive Theory and collectivism (i.e., social connectedness, sense of belonging, and community cohesion). We will conduct two focus groups of sedentary African-American women (n=16) to seek feedback on the intervention strategies (e.g., yoga sequences).

Aim 2: Assess feasibility of a hatha and restorative yoga intervention (n=30) compared to a control group (n=30). We will examine feasibility of participant recruitment, retention and adherence; fidelity of intervention delivery; and intervention materials.

Aim 3: Evaluate the acceptability and safety of a hatha and restorative yoga intervention (n=30) compared to a control group (n=30). We will examine the acceptability of intervention location and strategies, class format, enjoyment of sessions, and safety of the intervention.

Aim 4: To test feasibility and appropriateness of the targeted outcomes (i.e., primary: sedentary behavior and secondary: blood pressure and stress) for subsequent trials. It is important to properly measure expected outcomes but not make comparisons between intervention and control groups.

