### **3.0 Study Endpoints/Events/Outcomes**

#### **3.1 Primary Endpoint/Event/Outcome:**

This is a feasibility study, therefore the primary endpoints of interests are related to feasibility and acceptability of the intervention.

- Feasibility: Recruitment of participants - 200 women recruited and screened; 76 women (16 for Aim 1 focus groups and 60 for pilot intervention) enrolled and consented
- Feasibility: Retention and adherence -  $\geq 80\%$  of intervention participants attend  $\geq 80\%$  of intervention sessions
- Feasibility: Fidelity of intervention delivery -  $\geq 90\%$  of each videotaped session is delivered as planned based on training
- Feasibility: Intervention materials and resources - 100% of intervention materials and resources are delivered as planned
- Feasibility: Assessment measures -  $\geq 80\%$  intervention and control participants rate the assessments as not too burdensome;  $\geq 90\%$  intervention and control participants will complete baseline, post-intervention and 3-month follow-up assessments
- Acceptability: Intervention location, in-person classes, instructors, home-based resources -  $\geq 90\%$  intervention participants rate the various intervention components as acceptable
- Acceptability: Yoga intervention -  $\geq 90\%$  intervention participants rate intervention acceptable
- Safety: Adverse events - Zero severe adverse events (causes major disruption to participant's life, e.g., sprain, broken bone, CV event, death), zero moderate adverse events (causes minor inconvenience to participant, e.g., fainting spell, sore muscles for more than 3 days) and  $<10\%$  of participants report mild adverse events (no major impact, e.g., headache, sore muscles for 2-3 days)

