## 5.0 Procedures Involved

### 5.1 Study Design:

Our proposed feasibility study will be two-arm, RCT with 60 participants randomly assigned to either an intervention group (n=30) or control group (n=30).

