## **11.0 Number of Participants**

### **11.1 Number of Participants to be Consented:**

For formative assessment focus groups, a maximum number of 16 (minimum of 12) participants will be enrolled for an average of 6-8 participants for each of the two focus groups.

For the pilot RCT, a maximum number of 60 (minimum of 54) participants will be enrolled for an average of 27-30 participants for each of the intervention and control groups. Participants enrolled in the intervention condition will be consented to participate in the yoga intervention eligible and the post-intervention focus groups.

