**Aim 4. Targeted Outcomes.** Per the NCCIH’s “Pilot Studies: Common Uses and Misuse”, the research team do not intend to evaluate the efficacy of the intervention. The behavioral and biological outcome data will be used to inform the design of the future trial by identifying feasibility/adherence problems with measures and suggesting effect size expectations. Data will be cleaned for errors and outliers, checked for normality, and transformed if necessary. The primary behavioral outcome will be time spent sitting/lying down from the activPAL3 as the gold standard measure of sedentary time. The research team will also analyze standing, stepping, sit-stand transitions, and moderate and vigorous physical activity data from the activPAL. Blood pressure (systolic and diastolic average of three measurements), perceived stress, anthropometry and other exploratory measures will be analyzed similarly. If **missing data** exceed 10% multiple imputation will be performed in addition to complete case analysis. For this pilot, we will report 95% confidence intervals.

Proposed statistical analyses are outlined above.

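### Aim 4 should pass the SD, correlation and attrition to the next trial rather than an effect size, which 27–30 women per arm cannot locate and which Section 1.1 rules out by barring group comparisons

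*Combined protocol and SAP*

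**What the plan says.** Section 17.1 (Aim 4) states that "the research team do not intend to evaluate the efficacy of the intervention". It then names two uses of the behavioral and biological data for the future trial: "identifying feasibility/adherence problems with measures and suggesting effect size expectations". It promises 95% confidence intervals, but gives no SD, target difference, power or rule for sizing that trial.

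Section 1.1 says under Aim 4: "It is important to properly measure expected outcomes but not make comparisons between intervention and control groups".

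Section 5.1 describes a "two-arm, RCT with 60 participants randomly assigned to either an intervention group (n=30) or control group (n=30"). Section 11.1 allows fewer: "a maximum number of 60 (minimum of 54) participants will be enrolled for an average of 27-30 participants for each" arm.

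On data handling, Section 17.1 says: "Data will be cleaned for errors and outliers, checked for normality, and transformed if necessary". It does not define an outlier, say what is done with one, or plan a sensitivity analysis.

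**The concern.** Two parts of the plan pull against each other. The effect on which a two-arm trial is sized is the difference between the arms, and Section 1.1 says that difference is not to be examined. A within-arm change could be reported without comparing groups, but it is not the quantity that sizes a two-arm trial.

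Even without that conflict, arms of this size give a very wide interval for a between-group effect. A designer who takes the point estimate as the expectation could plan a trial several times too small or too large. The pilot can estimate the spread much better, yet the plan does not name the SD or the baseline-to-later correlation as outputs. It computes completion of assessments, but only against a benchmark and not as a planning input.

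The cleaning sentence matters for the same reason. An SD is useful for planning only if genuine extreme values are still in it and it is on the scale on which the next trial will be planned.

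**Working it through.** The plan has no precision or sample-size figure to reproduce, so what follows is an illustration.

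**Inputs from the documents.** 30 per arm (Section 5.1) and 27 per arm at minimum enrolment (Section 11.1). Section 3.1 sets a benchmark that at least 90% of "intervention and control participants will complete baseline, post-intervention and 3-month follow-up assessments". That leaves about 0.90 × 30 = 27, or 0.90 × 27 ≈ 24, per arm with complete data.

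**Assumptions, not in the documents.** Observed standardized difference d = 0.40, with positive values meaning benefit; next trial at two-sided 5% and 80% power; unadjusted comparison; normal data.

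**1. Precision of the effect size.** SE(d) = √(2/n + d²/(4n)).

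- n = 30: √(0.0667 + 0.0013) = 0.261; 95% CI 0.40 ± 1.96 × 0.261 = -0.11 to 0.91.
- n = 27: √(0.0741 + 0.0015) = 0.275; 95% CI -0.14 to 0.94.
- n = 24: √(0.0833 + 0.0017) = 0.292; 95% CI -0.17 to 0.97.

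**2. What that means for the next trial.** The approximate size per arm is 2 × (1.96 + 0.84)²/d², which gives 19.0 at d = 0.91 and 98.1 at d = 0.40. The exact two-sample t calculation gives:

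| d in the next trial | n per arm |
|---|---|
| 0.91 (upper limit) | 20 |
| 0.40 (point estimate) | 100 |
| 0.10 (a value inside the interval) | 1,571 |
| -0.11 (lower limit) | none; wrong direction |

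In 200,000 simulated pilots of 30 per arm with a true d of 0.5, each next trial was sized for 80% power on the observed d. Its true power fell between 70% and 90% in only about 20% of pilots. With a true d of 0.3 the figure was about 12%.

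**3. Precision of the spread.** The limits for a pooled SD are √(df/χ²) times the estimate, with df = 2n - 2.

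- n = 30 (58 df): 0.847 to 1.222, that is -15% to +22%.
- n = 27 (52 df): 0.839 to 1.237, that is -16% to +24%.

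**4. If genuine extremes were deleted.** For normal data cut at ±k SD, the remaining SD is that of a truncated normal. Required n varies with the SD squared.

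| Cut | SD multiplied by | Variance multiplied by | Required n understated by |
|---|---|---|---|
| 2 SD | 0.88 | 0.774 | 23% |
| 2.5 SD | 0.95 | 0.911 | 9% |
| 3 SD | 0.99 | 0.973 | 3% |

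A trial planned for 80% power at d = 0.5 would then have about 70%, 77% and 79.5% power. If only recording errors are corrected, this bias does not arise.

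**The case against.** The plan is cautious. It speaks of suggesting expectations, disclaims efficacy, promises 95% confidence intervals, and nowhere says the next trial will be sized on the point estimate. All of that stands, and it limits the conclusion to what could happen. But an interval only discloses imprecision; it does not say what the designer is to do with it.

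Adjusting for baseline would narrow the interval. With an assumed correlation of 0.7, SE = √(0.0667 × 0.51 + 0.0013) = 0.188 and the interval is about 0.03 to 0.77. That is a real gain, but still too wide for sizing a trial.

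A reader might infer that the plan deletes genuine outliers and hands on a spread that is too small. The documents do not support this. Cleaning can mean checking or flagging, no cut-off is given, and no passage says that an SD is carried forward. Nor would a trimmed SD be too small every time. In simulated normal pilots of 30 per arm, the trimmed pooled SD still exceeded the true SD in about 14% of pilots with a 2 SD cut and 45% with a 3 SD cut, against about 47% untrimmed. The bias is an average one, and it is negligible at 3 SD.

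Transformation is not wrong in itself; a log scale may suit salivary cortisol. Attrition is also partly covered, because Section 17.1 computes completion and looks to the future trial when benchmarks are missed.

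**Conclusion.** The point holds for the effect size. Sections 1.1 and 17.1 conflict on whether a between-group contrast is to be formed, and 27–30 per arm cannot locate one well enough to size a trial. In the illustration, one pilot interval covers next trials from about 20 per arm to no workable size, while the SD is known to about -15% to +22%. The conflict rests on the text alone. The figures rest on an assumed d of 0.40, 80% power, two-sided 5%, normal data and no baseline adjustment.

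It would go too far to say that the next trial will be mis-sized, because the plan states no sizing rule. It could be, if the point estimate is used.

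The outlier sentence is a secondary gap in specification. Its possible cost runs from 3% to 23% of the required sample size for normal data, depending on a rule the plan does not give.

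**What to change.** In Section 17.1, keep the purpose of identifying problems with the measures and replace the effect-size clause with wording such as:

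> estimating the SD, the correlation between baseline and later values, and attrition, each with a 95% CI; the target difference for the future trial will be set on relevance, not on the pilot's observed effect.

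This also brings Section 17.1 into line with the no-comparison statement in Section 1.1.

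Replace the cleaning sentence with wording such as:

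> Only verified errors or impossible values are removed; genuine extreme values are kept. SDs for planning are reported on the original scale, alongside any transformed analysis.

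The cost is wording only, with no new data or visits. The planning SD may come out slightly larger, and the pilot will offer no effect size, so the next trial's team must justify its target difference on other grounds.

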#### 17.2 Data Integrity:

There are two PIs for this study and the leadership plan helps to maintain the integrity of this study. [name] will be responsible for overseeing intervention development, implementation, and qualitative evaluation and will not be involved with data collection and analyses. [name], along with our analyst and biostatistician, will lead quantitative data collection and analyses at baseline, post-intervention, and 3-month follow-up and will be blinded to the intervention conditions.

### 18.0 Health Information and Privacy Compliance

#### 18.1 Select which of the following is applicable to your research:

- My research does not require access to individual health information and therefore assert HIPAA does not apply.
- I am requesting that all research participants sign a HIPCO approved HIPAA

Disclosure Authorization to participate in the research (either the standalone form or the combined consent and HIPAA Authorization).

- I am requesting the IRB to approve a Waiver or an alteration of research participant authorization to participate in the research.

Appropriate Use for Research: N/A

- An external IRB (e.g. Advarra) is reviewing and we are requesting use of the authorization language embedded in the template consent form in lieu of the U of M stand-alone HIPAA Authorization. Note: External IRB must be serving as the privacy board for this option.

18.2 Identify the source of Private Health Information you will be using for your research (Check all that apply)

- I will use the Informatics Consulting Services (ICS) available through CTSI (also referred to as the University's Information Exchange (IE) or data shelter) to pull records for me
- I will collect information directly from research participants.
- I will use University services to access and retrieve records from the Bone Marrow Transplant (BMPT) database, also known as the HSCT (Hematopoietic Stem Cell Transplant) database.
- I will pull records directly from EPIC.
- I will retrieve record directly from axiUm / MiPACS
- I will receive data from the Center for Medicare/Medicaid Services
- I will receive a limited data set from another institution
- Other. Describe: N/A

18.3 Explain how you will ensure that only records of patients who have agreed to have their information used for research will be reviewed.

N/A

18.4 Approximate number of records required for review:

N/A

18.5 Please describe how you will communicate with research participants during the course of this research. Check all applicable boxes.

N/A

- This research involves record review only. There will be no communication with research participants.

- Communication with research participants will take place in the course of treatment, through MyChart, or other similar forms of communication used with patients receiving treatment.
- Communication with research participants will take place outside of treatment settings. If this box is selected, please describe the type of communication and how it will be received by participants.

#### 18.6 Access to participants

N/A

#### 18.7 Location(s) of storage, sharing and analysis of research data, including any links to research data (check all that apply).

- In the data shelter of the [Information Exchange \(IE\)](#)

Store       Analyze       Share

- In the Bone Marrow Transplant (BMT) database, also known as the HSCT (Hematopoietic Stem Cell Transplant) Database

Store       Analyze       Share

- In REDCap (recap.ahc.umn.edu)

Store       Analyze       Share

- In Qualtrics (qualtrics.umn.edu)

Store       Analyze       Share

- In OnCore (oncore.umn.edu)

Store       Analyze       Share

- In the University's Box Secure Storage (box.umn.edu)

Store       Analyze       Share

- In an AHC-IS supported server. Provide folder path, location of server and IT Support Contact: Epidemiology & Community Health secured encrypted server managed by [name] ([[contact]](mailto:[contact])):

\\files.epi.umn.edu\[name]\YogaMoves

Store       Analyze       Share

- In an AHC-IS supported desktop or laptop.

Provide UMN device numbers of all devices:

Store       Analyze       Share

Other.

Indicate if data will be collected, downloaded, accessed, shared or stored using a server, desktop, laptop, external drive or mobile device (including a tablet computer such as an iPad or a smartform (iPhone or Android devices) that you have not already identified in the preceding questions

- I will use a server not previously listed to collect/download research data
- I will use a desktop or laptop not previously listed
- I will use an external hard drive or USB drive ("flash" or "thumb" drives) not previously listed
- I will use a mobile device such as an tablet or smartphone not previously listed

N/A

#### 18.8 Consultants. Vendors. Third Parties.

N/A

#### 18.9 Links to identifiable data:

As participants are enrolled in the study, they will receive a unique identifier that will be attached to all of their research materials (i.e., data collection and assessments, intervention materials). A password-protected document will contain identifying information and will only be accessible by authorized research staff will have access to subject identities. In accordance with NIH guidelines (i.e., the funding agency), identifiable data will be destroyed 5 years after the conclusion of the study.

#### 18.10 Sharing of Data with Research Team Members.

Electronic files will be stored in the University's Box Secure Storage and only authorized research staff will have access to a given file (i.e., measurement staff, but not intervention staff, will be able to access baseline data files).

#### 18.11 Storage and Disposal of Paper Documents:

We do not anticipate any paper documents as we will use electronic forms only. However, in the case that we have to use paper documents, we will keep all paper data collection forms in locked filing cabinets housed in the School of Kinesiology or Division of Epidemiology and Community Health and will destroy 5 years after the conclusion of the study.

### **19.0 Confidentiality**

#### 19.1 Data Security:

All data collected, especially participant information, during the study will be treated with strict confidentiality. Information will be entered into our data files by coded numbers (without recording individual names), thus assuring anonymity. Only authorized research staff will have access to participant identities or condition allocation (i.e., [name] and the measurement team will be blind to condition allocation). When the research team reports study results,

participants will not be named or identified in any way. All research team members have (or will) completed human subjects training.

Yoga classes will be recorded as part of the intervention and will be stored on a password-protected, view-only Google Drive. Videos will focus on instructors, with the goal of keeping participants out of the frame. Instructors will sign a video release form and participants will consent to being recorded in case of audio being picked up on the video. Only the research team and participants in the pilot RCT will have access to the catalog of yoga videos. No identifiable information will be shared over the videos.

## **20.0 Provisions to Monitor the Data to Ensure the Safety of Participants**

### **20.1 Data Integrity Monitoring.**

Drs. [name] and [name] will be responsible for monitoring the safety of this study, executing the Data and Safety Monitoring Plan (DSMP), complying with any reporting requirements, and consulting with the DSMB about any adverse events that may occur. If funding agency-mandated DSMB will receive formal reports from the research staff twice per year. The DSM report will include the participants' socio-demographic characteristics, expected versus actual recruitment rates, retention rates, quality assurance, or regulatory issues that occurred during the past year, a summary of Adverse Events (AEs) and Serious Adverse Events (SAEs) and any actions or changes with respect to the protocol. The DSM report will also include, when available, the results of any interim outcome analyses. In addition to the annual DSM report, the PIs will be responsible for informing NIH of any IRB actions within two weeks of their occurrence as well as any substantial changes or amendments to the study protocol prior to their implementation.

### **20.2 Data Safety Monitoring.**

No Adverse Events (AEs) or Serious Adverse Events (SAEs) are expected as a result of the study procedures or intervention. If any AEs or SAEs occur during the study, they will be documented by the research staff and reviewed by UMN IRB and DSMB to determine if further action needs to be taken. Quality control videos will be collected biweekly (i.e., every other week – weeks 2, 4, 6, 8, 10, 12). Although these videos are intended to make sure yoga instructors are following the training protocol, the research staff will be able to use the videos to identify any participants who may be performing yoga poses that could put her at an increased risk for injury. Yoga instructors will review and correct any injury risks participants. Please note that all yoga instructors will be 200-hour certified (Yoga Alliance registered) with current CPR certification and at least one year experience teaching yoga. The yoga proposed for this pilot intervention will be a combination of hatha and restorative yoga, which is lower intensity and typical for beginner yoga practitioners. Additionally, the instructors will be trained on the pilot study's yoga protocol by three experienced yoga teachers: two 500-hour and one 250-hour certified yoga teachers.

## **21.0 Compensation for Research-Related Injury**

### 21.1 Compensation for Research-Related Injury:

This research does not involve greater than minimal risk to participants.

### 21.2 Contract Language:

N/A

## **22.0 Consent Process**

### 22.1 Consent Process (when consent will be obtained):

This study will have two separate consent processes. Participants engaged in the formative assessment focus groups will be consented to complete those focus groups only. Participants enrolled in the pilot RCT will be consented to: a) participate in the study and to be randomized to either the intervention or control condition, and b) participate in the post-intervention focus groups, if allocated to the intervention group. After a participant is screened and identified as having met the eligibility criteria, participants will be asked to “consent and sign” the informed consent form. This will take place virtually for the formative assessment focus groups and in-person for the pilot RCT.

